## LIST OF ABBREVIATIONS AND DEFINITIONS OF TERMS

Abbreviation	Term
/	Per
%	Percent
°C	Degrees Celsius
°F	Degrees Fahrenheit
1, 25(OH)2D	1, 25 dihydroxyvitamin D
25(OH)D	Vitamin D
AE	Adverse Event
AESI	Adverse Event of Special Interest
ALP	Alkaline Phosphatase
ALT/ALAT (SGPT)	Alanine Aminotransferase (Serum Glutamic Pyruvic Transaminase)
approx	Approximately (or use 'about', not C. or ca.)
AST/ASAT (SGOT)	Aspartate Aminotransferase (Serum Glutamic Oxaloacetic Transaminase)
AUC	Area under Curve
BID	Twice Daily (Latin: bis in die)
BP	Blood Pressure
BSA	Body Surface Area
BUN	Blood Urea Nitrogen
CDMS	Clinical Data Management System
CI	Confidence Interval
C max	Maximum Concentration
C min	Minimum Concentration
C t	Pre-dose Plasma Concentration
CNS	Central Nervous System
C 0	Trough Levels
CRA	Clinical Research Associate
CRO	Contract Research Organization
CSO	Clinical Safety Officer
CSR	Clinical Study Report
CV	Coefficient of Variation
DC	Discontinuation
DMP	Data Management Plan
eCRF	Electronic Case Report Forms

Abbreviation	Term
e.g.	For Example (Latin: exempli gratia )
Eq	Equivalent (e.g., as in milli equivalent [mEq])
ET	Early Termination
etc	Et cetera
EU	European Union
Eur. Ph. or EP	European Pharmacopoeia
FDA	Food and Drug Administration
GCP	Good Clinical Practice
GGT	Gamma Glutamyl Transferase
GI	Gastro-intestine
Hb	Hemoglobin
Hct	Hematocrit
HIPAA	Health Insurance Portability and Accountability Act of 1996
ICF	Informed Consent Form
ICH	International Conference on Harmonisation
i.e.	That is
IEC	Institutional Ethics Committee
IGA	Investigator's Global Assessment of Disease Severity
IRB	Institutional Review Board
IRT	Interactive Response Technology
ITT	Intent-to-treat
IU	International Units
IUD	Intrauterine Device
IV	Intravenous
LOCF	Last Observation Carried Forward
MedDRA	Medical Dictionary for Regulatory Activities
mL	Milliliter
N/A	Not Applicable
NDA	New Drug Application
NF	National Formulary
N or n	Number
p	Probability (as in significance level)
P	Page(s)
PD	Pharmacodynamics
PE	Physical Examination
PIPEDA	Personal Information Protection and Electronic Documents Act

Abbreviation	Term
PK	Pharmacokinetics
PO	Oral
PP	Per-Protocol
PT	Preferred term
PTH	Parathyroid hormone
PUVA	Psoralen-ultraviolet-light
PR	Pulse Rate
RBC	Red blood cell
SAE	Serious Adverse Event
SAP	Statistical Analysis Plan
SAS	Statistical Analyses System
SD	Standard Deviation
SEM	Standard Error of Mean
SIN	Subject Identification Number
SGOT (AST)	Serum glutamic oxaloacetic transaminase
SGPT (ALT)	Serum glutamic pyruvic transaminase
SOC	System Organ Class
SOP	Standard Operating Procedure
$t_{1/2}$	Half-life
TEAE	Treatment Emergent Adverse Event
$t_{max}$	Time to Maximum Concentration
UA	Urinalysis
ULN	Upper Limit of Normal
UPT	Urine Pregnancy Test
US	United States
USP	United States Pharmacopeia
UV	Ultraviolet light
WBC	White Blood Cell

## 1 BACKGROUND AND RATIONALE

Psoriasis vulgaris is one of the most common chronic skin diseases with a prevalence estimated at between 1.4% and 2.9% of the population. In approximately 35% of adults with psoriasis, the onset occurred in childhood (Farber 1999). In pediatric subjects and adolescents, plaque psoriasis is the most common form encountered, ranging from 34% to 84% in frequency and followed by guttate or “drop-like” psoriasis in 25% of cases (Lewkowicz 2004 and Nanda 1999).

Vitamin D derivatives are well-established, efficacious and safe topical drugs used in the therapy of chronic psoriasis. In the USA, only calcipotriol and calcitriol are on the market; they are indicated for the treatment of mild to moderate plaque psoriasis in adults. The earliest approvals of calcitriol 3 mcg/g ointment occurred in 1995 in The Netherlands and Switzerland. To date, calcitriol 3 mcg/g ointment is approved in 39 countries. It is marketed as Silkis® ointment in 30 countries worldwide, including most European countries. Calcitriol 3 mcg/g ointment was approved in the USA on January 23, 2009 (Vectical®, Galderma Laboratories).

A total of 45 clinical studies have been conducted by the Sponsor to evaluate calcitriol ointment at various concentrations. To date, 2974 subjects have been treated with calcitriol as part of the drug development program. Calcitriol 3 mcg/g ointment has been shown to be effective and safe, without affecting calcium homeostasis parameters in adult subjects. Clinical studies have also shown that calcitriol is less irritating than calcipotriol.

Two pivotal Phase 3 studies (SPR.18053 and SPR.18054) with calcitriol 3 mcg/g ointment were completed in 2002. In both studies, the primary endpoint (Success Rate) was clinically and statistically superior for calcitriol 3mcg/g ointment compared to vehicle at Week 8. The superiority of treatment with calcitriol over vehicle was observed as early as Week 2, and sustained throughout the treatment period of 8 weeks.

A PK/PD study (SPR.18102) was conducted from August 2006 to September 2009 on 25 adolescents (12-17 years old; mean age: 14.7 years) with plaque psoriasis affecting 10 to 35% BSA (mean: 17.8%). Serum calcitriol levels were investigated at baseline and after 21 days of treatment with Vectical® (calcitriol 3µg/g ointment). Subjects received two applications per day and up to 15 g of formulation per application, depending on the total BSA and on the percentage of psoriasis-involved BSA. There was no significant variation of calcitriol levels during treatment. The overall mean ( $\pm$ SD) value of maximum calcitriol plasma levels (Cmax) was 76 $\pm$ 24 pg/mL at Baseline (endogenous levels) and 73 $\pm$ 22 pg/mL after 3 weeks of treatment. Regarding age stratification, the mean Cmax and AUC0-9hr or AUC0-12hr at Baseline were higher in the 12 to <15 years than in the 15 to 17 years (respectively 26% higher for Cmax and 19% higher for AUC0-9hr and AUC0-12hr). The same tendency was observed after 21 days of application. The plasma calcitriol levels (Cmax) appeared to be 21% higher in the 12 to <15 years age group compared to the 15 to 17 years age group and AUC0-9hr and AUC0-12hr, were approximately 17% higher. However, in each stratum, the calcitriol levels after 21 days of treatment were similar to the baseline levels. Overall, the repeated application of calcitriol 3 µg/g ointment did not result in an increased systemic exposure.

Furthermore, no correlation could be established between percentage of psoriasis-involved BSA and  $AUC_{0-9h}$  in this study. Therefore, in study 18131, repeated applications of Vectical® are not expected to increase endogenous levels of calcitriol.

As a result of the discussion with the Agency in July 2015, the ongoing long-term safety study (SPR.18131) is being amended to include a PK assessment in a subset of 9 children aged 2 to 6 years and 11 months old and the 2 ongoing studies (SPR.18104 and SPR.18132) will be closed to subject enrollment. These decisions were suggested and agreed by the Agency for logistical reasons and were not based on any safety concerns regarding the product's use in children.

A summary and rationale of the present amendment follows:

- Inclusion of PK assessments in this long-term safety study. In discussion with FDA, it was agreed that a Pharmacokinetic assessment will be performed in approximately 9 subjects with plaque psoriasis aged 2 to 6 years and 11 months old with a minimum of 3% BSA involvement .
- Addition of serum PD assessment at Baseline for subjects in the PK group so that PK/PD relationships can be investigated.
- Number of enrolled subjects reduced from 140 to 100.
- Study visits at Week 8 and Week 20 were removed.
- Management of parathyroid hormone (PTH) results falling below the lower limit of normal was revised.

The Independent Data Monitoring Committee (IDMC) will supervise the subjects' safety as defined in the IDMC Charter. The IDMC will inform the Sponsor and suggest the action(s) to be taken, if safety signals are observed.

The specific roles of the IDMC include, but are not limited to:

- Meet periodically to review individual data and summary analyses,
- Assess data quality, including completeness,
- Monitor biochemical and pharmacodynamic parameters,
- Suggest additional data analyses,
- Maintain and document any decisions and activities taken during IDMC meetings,
- Recommend to the Sponsor whether recruitment/participation should be suspended for either individual participants or the entire study.

Further details regarding the IDMC's role and activities will be outlined in a separate IDMC Charter document.

### **1.1 Medical background and short rationale for the clinical trial**

Safety and efficacy of calcitriol 3 mcg/g ointment in pediatric subjects under the age of 12 has not been previously studied. The current study of the long-term safety of calcitriol 3 mcg/g ointment applied twice daily for up to 26 weeks is specifically designed to enroll and evaluate pediatric subjects 2 to 16 years and 11 months (Version R03) of age with mild to moderate plaque psoriasis. In addition, this study will allow the evaluation of plasma concentrations of calcitriol in a subset of 9 subjects aged 2 to 6 and 11 months.

### **1.2 Drug profile**

Calcitriol is the naturally occurring and biologically active metabolite of vitamin D3. Calcitriol inhibits the proliferation and stimulates differentiation of keratinocytes. It inhibits the proliferation of T-cells and normalizes the production of various inflammation factors. For these reasons, calcitriol is an effective drug in the topical treatment of psoriasis.

At the time of writing this amended protocol, there have been no recent updates to the reference safety information for Vectical®/Silkis™, nor are any updates pending.

### **1.3 Risk/Benefit assessment**

As mentioned in Section 1 above, calcitriol 3 mcg/g ointment has shown efficacy over vehicle in studies with adult subjects.

The primary objective of this LTS study is to collect long-term (up to 26 weeks) safety data in children 2-16 years and 11 months of age (Version R03). As a secondary objective, calcitriol levels will be assessed at several time points throughout the study duration in a subset of children aged 2 to 6 years and 11 months old.

As mentioned in Section 1, childhood psoriasis is very prevalent, and an alternative to topical corticosteroid therapy in a pediatric population would be a desirable option. Calcitriol is a corticosteroid-sparing treatment that does not cause known steroid-related side effects such as skin atrophy and hypothalamo-pituitary axis (HPA) suppression.

PK/PD data from adolescent subjects 12-17 years of age in study SPR.18102 are mentioned in Section 1 above, including abnormalities observed in PTH levels in a subset of subjects. PTH will be monitored regularly throughout this study and all abnormal values and downward trends will be reviewed by the study Medical Expert and/or CSO. In addition, an IDMC will be in place for the duration of the study and will monitor laboratory and pharmacodynamic data as defined in the IDMC Charter.

In controlled clinical trials in adults, hypercalcemia was observed in 24% (18/74) of subjects exposed to calcitriol 3 mcg/g ointment, and in 16% (13/79) of subjects exposed to vehicle. However, the increases in calcium and albumin-adjusted calcium levels were less than 10% above the upper limit of normal.

In the two pooled 8-week vehicle-controlled studies in 419 adult subjects, pruritus and discomfort pain were reported in 1% and 3% respectively for subjects treated with calcitriol 3 mcg/g ointment, and 1% and 2% respectively for subjects exposed to vehicle.

In a 52-week open label study of 324 adult subjects, adverse events reported at a rate of greater than or equal to 3% of subjects treated with calcitriol 3 mcg/g ointment were lab test abnormality (8%), urine abnormality (4%), psoriasis (4%), hypercalciuria (3%), and pruritus (3%). Kidney stones were reported in 3 subjects and confirmed in two.

All subjects enrolled in this LTS study will receive active treatment, calcitriol 3 mcg/g ointment. There is a risk of local irritation reactions, hypercalcemia, hypercalciuria and kidney stones associated with study participation. Multiple safety measures including regular monitoring of serum hematology, biochemistry and pharmacodynamic parameters pertaining to calcium homeostasis, as well as urine testing have been implemented to closely monitor subject safety. Further details regarding safety assessments are provided in Section 2.1.

## 2 CLINICAL TRIAL OBJECTIVES AND CLINICAL HYPOTHESIS

### 2.1 Clinical trial objectives

#### Safety Objectives:

The primary objective of this study is to evaluate the safety of up to 26 weeks of treatment with calcitriol 3 mcg/g ointment when used twice daily, without occlusion, to treat pediatric subjects (2 to 16 years and 11 months of age, Version R03) with mild to moderate plaque psoriasis. As a secondary objective, calcitriol plasma levels will be assessed at several time points throughout the study duration in a subset of children aged 2 to 6 years and 11 months old.

#### Safety Assessments:

- Adverse Event recording at each study visit.
- An Independent Data Monitoring Committee (IDMC) will be established for this study and will be responsible for securing the subjects' safety including the review of the subjects' laboratory results for: parathyroid hormone, calcium, phosphorus, albumin, and creatinine levels on an ongoing basis (as defined in the IDMC charter). The IDMC will inform the Sponsor and recommend actions to be taken, if safety signals are observed.
- Systemic Safety Parameters to be completed per the Schedule of Assessments (Table 2).
  - Vital signs (blood pressure and pulse rate)
  - Physical examination (weight, skin, cardiovascular, respiratory, abdomen, head and neck, gastrointestinal, respiratory, musculoskeletal, neurological, lymph nodes and psychological). Height is to be evaluated at the Screening visit only.
  - Routine safety laboratory parameters
    - *Hematology*: red blood cells, white blood cells with differential cell count, hemoglobin, hematocrit, platelets
    - *Blood chemistry (non fasting)* : total protein, ALT (SGPT), AST (SGOT), alkaline phosphatase, blood urea nitrogen, creatinine (calculated creatinine clearance), total and conjugated bilirubin
    - *Urinalysis*: glucose, ketone, blood, protein, nitrite and leukocytes
  - Pharmacodynamic parameters
    - *Serum(non fasting)*: calcium, phosphorus, albumin (in order to calculate the serum albumin-adjusted calcium), PTH
    - *Urine*: Urine calcium and creatinine on 24-hour urine collection, whenever possible, or a urine sample after fasting for 4 hours in order to calculate Urine calcium : creatinine ratio. Subjects that are toilet-trained should be actively encouraged to complete the 24-hour urine collection.

- Other Assessments
  - 1, 25(OH)2D.
  - 25(OH)D.
  - *Urine Pregnancy Test for post menarcheal females (including subjects who become post-menarcheal during study participation).*

### **Efficacy Objectives:**

To evaluate the long-term efficacy of up to 26 weeks of treatment with calcitriol 3 mcg/g ointment when used twice daily, without occlusion, to treat pediatric subjects (2 to 16 years and 11 months of age, Version R03) with mild to moderate plaque psoriasis.

### **Efficacy Assessments:**

- Investigator's Global Assessment of Disease Severity (Will be referred to as the IGA score in this document) [IGA scale is described in Section 7.1.1.1].
- Pruritus.

### **Pharmacokinetic (PK) Assessment:**

- Plasma concentration of calcitriol (1, 25(OH)2D) will be assessed using a single pre-dose blood sample ( $C_t$ ) in a subset of approximately 9 subjects aged between 2 to 6 years and 11 months old.

### **Other Assessments:**

- Percent Body Surface Area (BSA) involved.
  - The % BSA involved will be assessed using the methodology shown in Section 13.3, Appendix 3.

## 2.2 Clinical hypothesis

Long term use (26 weeks) of calcitriol 3 mcg/g ointment is safe and efficacious in pediatric subjects (2 to 16 years and 11 months of age, Version R03) with mild to moderate plaque psoriasis.

The calcitriol absorption in pediatric subjects (2 to 6 years and 11 months of age) is expected to be comparable to that in adults and adolescents, with no significant impact on calcium/phosphorus metabolism.

## 3 OVERALL CLINICAL TRIAL DESCRIPTION

This is an open-label, uncontrolled, multicenter long-term safety and efficacy study in pediatric subjects (age 2-16 years and 11 months, Version R03) with mild to moderate plaque psoriasis.

Approximately one hundred (100) subjects will be enrolled into this study. A subset of enrolled subjects (approximately 9 among the 100) will meet the PK requirements: pediatric subjects aged 2 to 6 years and 11 months (inclusive at Screening) and with a minimum 3% BSA involvement.

Qualified subjects will receive calcitriol 3 mcg/g ointment for a period of up to 26 weeks. The subject's parent/legal guardian or the subject under the responsibility of the parent/legal guardian will apply a thin film of study drug as needed to cover all involved areas twice daily, without exceeding a maximum of 0.5 g/kg of body weight or 28 g daily (whichever is the lower). If the subject experiences complete clearing of psoriasis per physician assessment (i.e. an IGA of 0), the subject should discontinue the study drug but continue to follow the visit schedule through the Week 26 visit. Treatment with study drug should be resumed if the IGA score is >0 and <4.

Subjects will be evaluated at screening, baseline and Weeks 4, 12, 26, and 30 as described in the Schedule of Assessments (Table 2). A visit window of  $\pm 5$  days will be allowed for Baseline and a visit window of  $\pm 3$  days will be allowed at the visits from Weeks 4 through 30.

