 Subjects with suspected kidney stones should temporarily discontinue study drug and will be referred to their Primary Care Physician (PCP) for care in tandem with Sponsor consultation of the IDMC.

 The visit before: Distribute container and provide instructions for 24-hour urine collection to be started 1 day prior to Week 12 and Week 26/ET visits. The study site should contact the parent/legal guardian 48 hours prior to the visit to remind them to start the urine collection.

 Subjects may re-screen one time with written approval from the Sponsor prior to re-entry into the study.

 At Baseline, the study nurse show the subject's parents how to apply the drug.

 Visit window of  $\pm$  5 days.

 For subjects in the PK group, a single blood sample at Screening and Baseline will be taken, then a single pre-dose blood sample will be taken at Weeks 4, 12, 26 and 30, to assess the calcitriol plasma concentration. The volume of each blood sample will be 5 mL. A total volume of 30 mL will be collected during the study for PK assessment.

 Serum PD will be assessed during Baseline visit only for subjects 2 to 6 years and 11 months of age in whom PK analysis will be conducted in order to assess PK/PD relationships at Baseline for these subjects.

Unscheduled visit: When necessary and exceptionally, because of either an AE needing a specific treatment, AE leading to withdrawal from the study, laboratory result(s) that warrant further testing, or other reason.

An ongoing dialogue between subject, parent/legal guardian and investigators focusing on all aspects of the trial is encouraged. Any new information that arises in relation to the trial and that might affect the willingness of the subject and/or parent/legal guardian should be discussed. This brief discussion should be documented during each study visit.

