### **6.1.5 Instructions for use and administration**

The first dose will be applied under the supervision of the Investigator, at the Investigative site.

Application should be done either by the subject's parent / legal guardian or by the subject himself. It is the responsibility of the parent/legal guardian to decide if the subject can apply the product himself and if they should supervise the application depending on the capability of the child. After application, the study product tube should be stored out of the reach and the sight of children,

Application will consist of a thin film of study drug as needed to cover all involved areas twice daily (morning/evening), without exceeding a maximum of 0.5 g/kg of body weight or 28 g daily (whichever is the lower). The dosing calendar is to be completed by the subject or subject's parent or legal guardian daily and returned to the site at each visit.

For the subset of subjects with PK evaluations, the drug product MUST NOT be applied on the areas that will be used for blood sampling. These areas will be defined at screening by the Investigator.

In addition, at the week 4, week 12 and week 26 visits, study drug applications will be performed on site after the PK pre-dose blood sampling is obtained. This blood sample has to occur 12 hours ( $\pm 1$  hour) after the last product application.

To avoid potential contamination of the blood sample collected, study drug applications and blood draws must NOT occur in the same room. Additionally, the blood draw area should be clean and kept away from contact with study drug.

Subjects should wait at least six hours after the study treatment application before swimming or bathing.

Cetaphil® Moisturizing Cream or equivalent (provided by the Sponsor and distributed by the Investigator or designee at the Baseline Visit) may be used during the study as needed on non-treated areas of the skin. Cetaphil® Gentle Skin Cleanser or equivalent (provided by the Sponsor) may be used for cleansing.

Subjects will be permitted to use medicated shampoos that do not contain corticosteroids or vitamin D derivatives to treat scalp psoriasis. Tar products can be used on the face and scalp areas.

No other topical treatments, other than the test materials, will be permitted on the treated areas. However, emollients and sunscreen on healthy skin areas are permitted during the course of the study.

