### 7.4 Pharmacokinetic assessment

#### 7.4.1 Blood sampling

The systemic level of calcitriol will be assessed at each visit using a single blood sample ( $C_t$ ) according to the Schedule of Assessments (Table 2). To avoid tube contamination, drug product application and blood draws have to be performed in different rooms. Blood samples will have to be collected in either the morning or evening (to be determined at screening according to the subject's lifestyle). In addition, for the blood samples to be drawn during the treatment period (i.e. at Week 4, Week 12 and Week 26), the sampling has to occur 12 hours ( $\pm 1$  h) after the last product application. Blood sampling procedure and handling of samples will be described in a separate document.

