### **7.4.3 Pharmacokinetic measurements**

The pharmacokinetic analysis will be carried out by GALDERMA R&D, Sophia Antipolis, France. The  $C_t$  mean values and the standard deviation (SD), will be calculated and reported.

Assessments occurring at screening and baseline (before product application) will allow determining calcitriol endogenous levels variability. Pre-dose samples performed at Weeks 4, 12, and 26 will document the calcitriol plasma concentration during the treatment period. Blood sample drawn at week 30 visit allow determining the calcitriol plasma concentration one month after the last drug product application.

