### **9.1.2 Populations analyzed, evaluability and limitation / evaluation of bias**

Prior to the final database lock of the study, a data review will occur to assess the potential bias of any data issues for final statistical analyses; and to determine the final subject populations for statistical analyses. Decisions made from the data review will be documented and any changes to the SAP will be made before database can be locked.

The statistical analyses will be performed based on the safety population.

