### 9.1.6 Pharmacokinetics analysis

$C_t$  will be submitted after logarithmic transformation (Ln), to paired comparisons of Baseline and each subsequent time point. Ninety percent confidence intervals of the pairwise differences will be calculated using the Student's t statistic. The limits of the intervals will be back-transformed into exponential to obtain 90% confidence intervals of the ratios of geometric means between time points, on the original scale.

PK/PD relationships will be investigated by correlating  $C_t$  with appropriate PD parameters, using Spearman coefficient and graphical illustrations.

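### PK and laboratory samples taken after drug is stopped for clearing are analysed with on-drug samples, which could dilute any calcitriol or calcium effect by an unknown amount

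*Protocol*

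**What the plan says.** **Stopping rule.** For a child assessed as clear (IGA 0), Protocol 3 states that "the subject should discontinue the study drug but continue to follow the visit schedule through the Week 26 visit". Treatment restarts if the IGA is above 0 and below 4. Protocol 5.6 and 6.4 and SAP 2 repeat the rule.

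**PK.** Protocol Table 2, footnote 17, takes one sample at Screening and one at Baseline, "then a single pre-dose blood sample will be taken at Weeks 4, 12, 26 and 30". Protocol 7.4.3 gives the purpose: "Pre-dose samples performed at Weeks 4, 12, and 26 will document the calcitriol plasma concentration during the treatment period". The Week 30 sample is meant to show "the calcitriol plasma concentration one month after the last drug product application". Protocol 7.4.1 requires that at Weeks 4, 12 and 26 "the sampling has to occur 12 hours", give or take one hour, after the last application. Protocol 6.1.5 adds that at those visits "study drug applications will be performed on site after the PK pre-dose blood sampling is obtained". Protocol 9.1.6 submits log-transformed concentrations "to paired comparisons of Baseline and each subsequent time point", with 90% intervals. On the analysis set, 9.1.2 says: "The statistical analyses will be performed based on the safety population".

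**Laboratory.** SAP 7.3.3 tabulates Screening against Final, where Final is the last post-baseline value in the treatment period. SAP 7.5 assigns laboratory values by visit. Both schedules use treatment period as a heading over Baseline to Week 26/ET, whether or not drug is in use. Urine calcium and creatinine are collected at Screening, Week 12 and Week 26. At Week 30 they are collected for the PK group, and otherwise at the investigator's discretion.

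**The concern.** A child off drug since clearing cannot be sampled 12 hours after an application and should not receive the on-site dose afterwards. Neither document says whether that child's sample is skipped, excluded or flagged. Read as written, 9.1.6 pairs it with Baseline like any other. The laboratory tables do the equivalent.

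The primary objective is the safety of up to 26 weeks of treatment, and the secondary objective is calcitriol level in about 9 young children. Protocol 2.2 expects absorption comparable to that in adults and adolescents, without a material effect on calcium and phosphorus metabolism. Any dilution from off-drug samples favours that expectation, which in a safety study is the unsafe direction. The paired PK interval is also the only interval estimate planned. The data review before lock could set such samples aside, but in an open-label trial that choice would be made with the results already visible.

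**Working it through.** The plan states no figure for this point. Its one sample-size number, 167 screened for 100 enrolled, reproduces (100 / 0.60 = 166.7) and has no bearing here.

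**1. Time off drug, amended schedule.** Target days from SAP Table 2: Week 4 = 29, Week 12 = 85, Week 26 = 183. Entry IGA is 2 or 3, so Week 4 is the first scheduled visit at which drug can stop.

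| Clear at | Sampled at | Days off drug | Weeks |
|---|---|---|---|
| Week 4 | Week 12 | 85 − 29 = 56 | 8 |
| Week 12 | Week 26 | 183 − 85 = 98 | 14 |
| Week 4, no restart | Week 26 | 183 − 29 = 154 | 22 |

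The ±3-day windows move each gap by up to 6 days. Barring an unscheduled visit, the first row holds even for a child found to have relapsed at Week 12, because the restart follows that visit's IGA. The plan's own off-drug condition, Week 30, is 30 − 26 = 4 weeks, or 28 days. The gaps above are 2.0, 3.5 and 5.5 times that. For a child who stopped at Week 12 or Week 4 and never restarted, the Week 30 sample falls 18 or 26 weeks after the last application, not one month.

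**2. Original schedule.** Protocol 10.5.2 keeps subjects already enrolled on the original protocol, and SAP Table 1 has serum pharmacodynamics at Weeks 8 and 20. For them a laboratory gap can be 57 − 29 = 28 days, about 4 weeks. PK came in with the amendment, so the 8-week minimum stands for PK.

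**3. What is untouched.** Week 4 PK and serum values precede any scheduled stop for clearing. Urine calcium:creatinine, 25(OH)D and 1,25(OH)2D have no Week 4 sample.

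**4. Dilution of the PK ratio.** Assume *k* of 9 children are off drug and back at their own baseline. The observed ratio is then *r*^((9 − *k*)/9).

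| On-drug ratio *r* | *k* = 0 | 1 | 2 | 3 |
|---|---|---|---|---|
| 1.00 | 1.00 | 1.00 | 1.00 | 1.00 |
| 1.25 (assumed) | 1.25 | 1.22 | 1.19 | 1.16 |
| 1.50 (assumed) | 1.50 | 1.43 | 1.37 | 1.31 |

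The adolescent study in Protocol 1 gives mean maximum levels of 76 pg/mL at baseline and 73 after 21 days. Their ratio, 73/76 = 0.96, is close to the first row.

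**5. Against the precision available.** From that study, CV = 24/76 = 0.316, so the log SD is √ln(1 + 0.316²) = 0.308. With an assumed within-child correlation of 0, 0.5 or 0.8, the SD of paired log differences is 0.436, 0.308 or 0.195. The 90% limits are then the estimate divided and multiplied by exp(1.860 × SD/3) = 1.31, 1.21 or 1.13. Three of 9 off drug at *r* = 1.25 shifts the estimate by a factor of 1.25^(3/9) = 1.08, which is less than the interval's half-width in each case.

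**6. How likely is *k* ≥ 1?** No clearance rate is given. If 5%, 10%, 20% or 30% of children are off drug at a visit, the chance that at least one of 9 is off drug is 1 − (1 − *p*)⁹ = 37%, 61%, 87% or 96%. The chance of three or more is 5% at *p* = 10% and 26% at *p* = 20%.

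**7. Laboratory illustration.** Protocol 1.3 reports adult hypercalcemia of 24% on drug and 16% on vehicle. If that 8-point excess were all due to drug and disappeared off drug, shares of 5%, 10%, 20% and 30% off drug would leave 8 × (1 − *p*) = 7.6, 7.2, 6.4 and 5.6 points.

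**8. Compliance does not reveal it.** SAP 7.3.1.3 removes cleared days from expected exposure. A child off drug from Week 4 to Week 12 misses 56 of 182 days (31%) yet scores 126/126 = 100%.

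**The case against.** The best defence is that stopping when clear is part of the regimen under study, so by-visit results are valid for that regimen. This stands, and it is why the planned summaries should stay. It does not make a sample taken 14 weeks off drug a treatment-period concentration in the sense of 7.4.3.

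The documents' only pediatric PK evidence shows no rise in adolescents, and Protocol 1 expects none here. That stands too: at a ratio of 1.0 nothing is diluted. It does not settle the matter for ages 2 to 6, which the trial was amended to study.

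Safeguards exist. SAP 7.3.1.3 summarises reasons for and duration of interruptions, out-of-range values are listed, the IDMC is alerted to calcium and PTH abnormalities, and deviations are reviewed before lock. An on-drug calcium signal would be hard to miss entirely. None of these, however, links a PK or laboratory value to drug status at sampling.

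A reader might infer from the absence of a PK section in the SAP that the sponsor chose to pool off-drug samples. The documents do not support that. The SAP supplied describes the earlier design (140 subjects, Weeks 8 and 20), and the 12-hour rule points the other way. The gap is silence, not a stated choice.

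**Conclusion.** The gap is real and worth closing. Followed as written, the plan mixes off-drug with on-drug values in the Week 12 and Week 26 PK comparisons and in the Final laboratory shift. A child clear at Week 4 who stays off drug contributes no scheduled on-drug urine calcium:creatinine value.

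The effect on the results is conditional. It needs some children to clear completely and the drug to have a reversible effect, and the documents quantify neither. It runs from nil at a true ratio of 1.0 to a reading of 1.22 to 1.16 for an assumed 1.25, with 1 to 3 of 9 children off drug and back at baseline.

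Three stronger readings are tempting and unsupported. One is that the results will be biased toward no effect; that turns a condition into a fact. Another is to express the harm as a lost chance that the lower 90% limit exceeds 1; the plan sets no such criterion and describes the study as without inferential statistics. The third is that efficacy is compromised; the Week 26 efficacy values describe the stop-when-clear regimen and need no change.

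**What to change.** In Protocol 9.1.6 and the updated SAP:

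1. Derive time since last application for every PK and laboratory sample from the dosing calendar, which already records the date and time of each application (Protocol 6.3.4).
2. Keep the planned all-samples PK comparison. Add one limited to children on drug at sampling, meaning not stopped for clearing or another interruption. A strict 12 ± 1 hour filter would also drop treated children sampled slightly off time. Add a second comparison of Baseline with each child's last on-drug sample, so that children who clear are not selected out. List off-drug samples with days since last application.
3. Keep the Screening-versus-Final shift table and report the number off drug at Final by reason. Add a shift from Screening to the last on-drug value for albumin-adjusted calcium, phosphorus, PTH and urine calcium:creatinine, stating how many children have no on-drug urine value. A shift to the worst on-drug value may be added if labelled as an extreme of repeated measures.

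The cost is SAP text, one derived variable, two PK comparisons and one laboratory table, all from data already collected. The SAP needs updating for the amendment in any case. The downside is fewer than 9 pairs in the on-drug rows at Weeks 12 and 26 if any PK child has cleared.
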